6.3.1 Disease Parameters

At baseline, tumor lesions will be selected and categorized as target or non-target lesions, defined as described below.

All tumor measurements must be recorded in millimeters (or decimal fractions of centimeters).

A sum of the longest diameters (SLD) of the non-nodal target lesions will be calculated and reported as the baseline SLD.

6.3.1.1 Measurable disease

Measurable lesions are defined as those that can be accurately measured in at least one dimension (longest diameter to be recorded) as:

- By CT scan:
 - Scan slice thickness 5 mm or under: as ≥ 10 mm
 - Scan slice thickness >5 mm: double the slice thickness
- With calipers on clinical exam: ≥ 10 mm.

Malignant lymph nodes. To be considered pathologically enlarged and measurable, a lymph node must be ≥ 15 mm in short axis when assessed by CT scan (CT scan slice thickness recommended to be no greater than 5 mm). At baseline and in follow-up, only the short axis will be measured and followed.

Non-measurable disease. All other lesions (or sites of disease), including small lesions (longest diameter <10 mm or pathological lymph nodes with ≥ 10 to <15 mm short axis), are considered non-measurable disease. Bone lesions, leptomeningeal disease, ascites, pleural/pericardial effusions, lymphangitis cutis/pulmonis, inflammatory breast disease, and abdominal masses (not followed by CT or MRI), are considered as non-measurable.

Note: Cystic lesions that meet the criteria for radiographically defined simple cysts should not be considered as malignant lesions (neither measurable nor non-measurable) since they are, by definition, simple cysts.

‘Cystic lesions’ thought to represent cystic metastases can be considered as measurable lesions, if they meet the definition of measurability described above. However, if non-cystic lesions are present in the same participant, these are preferred for selection as target lesions.

6.3.1.2 Target lesions

Target lesions. All measurable lesions up to a maximum of 2 lesions per organ and 5 lesions in total, representative of all involved organs, should be identified as **target lesions** and recorded and measured at baseline. Target lesions should be selected on the basis of their size (lesions with the longest diameter), be representative of all involved organs, but in addition should be those that lend themselves to reproducible repeated measurements. It may be the case that, on occasion, the largest lesion does not lend itself to reproducible measurement in which circumstance the next largest lesion which can be measured reproducibly should be selected. A sum of the diameters (longest for non-nodal lesions, short axis for nodal lesions) for all target lesions will be calculated and reported as the baseline sum diameters. If lymph nodes are to be included in the sum, then only the short axis is added into the sum. The baseline sum diameters will be used as reference to further characterize any objective tumor regression in the measurable dimension of the disease.

Non-target lesions. All other lesions (or sites of disease) including any measurable lesions over and above the 5 target lesions should be identified as **non-target lesions** and should also be recorded at baseline. Measurements of these lesions are not required, but the presence, absence, or in rare cases unequivocal progression of each should be noted throughout follow-up.

6.3.2 Methods for Evaluation of Measurable Disease

All measurements should be taken and recorded in metric notation using a ruler or calipers. All baseline evaluations should be performed as closely as possible to the beginning of treatment and never more than 4 weeks before the beginning of the treatment.

The same method of assessment and the same technique should be used to characterize each identified and reported lesion at baseline and during follow-up. Imaging-based evaluation is preferred to evaluation by clinical examination unless the lesion(s) being followed cannot be imaged but are assessable by clinical exam.

Clinical lesions: Clinical lesions will only be considered measurable when they are superficial (e.g., skin nodules and palpable lymph nodes) and ≥ 10 mm diameter as assessed using calipers (e.g., skin nodules). In the case of skin lesions, documentation by color photography, including a ruler to estimate the size of the lesion, is recommended.

Chest x-ray: Lesions on chest x-ray are acceptable as measurable lesions when they are clearly defined and surrounded by aerated lung. However, CT is preferable.

Conventional CT and MRI: The RECIST 1.1 guidelines has defined measurability of lesions on CT scan based on the assumption that CT slice thickness is 5 mm or less. If CT scans have slice thickness greater than 5 mm, the minimum size for a measurable lesion should be twice the slice thickness.

MRI is also acceptable in certain situations (e.g., for body scans), as detailed per Section [2.4](#) and [6.3](#). As with CT, if an MRI is performed, the technical specifications of the scanning sequences used should be optimized for the evaluation of the type and site of disease. Furthermore, as with CT, the modality used at follow-up should preferably be the same as was used at baseline and the lesions measured/assessed on the same pulse sequence. Ideally, the same type of scanner should be preferably used and the image acquisition protocol should be followed as closely as possible to prior scans. Body scans should be performed with breath-hold scanning techniques, if possible.

PET/CT: At present, the low dose or attenuation correction CT portion of a combined PET/CT is not always of optimal diagnostic CT quality for use with RECIST measurements. However, if the site can document that the CT performed as part of a PET/CT is of identical diagnostic quality to a diagnostic CT (with IV and oral contrast), then the CT portion of the PET/CT can be used for RECIST measurements and can be used interchangeably with conventional CT in accurately measuring cancer lesions over time. Note, however, that the PET portion of the CT introduces additional data which may bias an investigator if it is not routinely or serially performed.

Ultrasound: Ultrasound is not useful in assessment of lesion size and **should not be used** as a method of measurement. Ultrasound examinations cannot be reproduced in their entirety for independent review at a later date and, because they are operator dependent, it cannot be guaranteed that the same technique and measurements will be taken from one assessment to the next. If new lesions are identified by ultrasound in the course of the study, confirmation by CT or MRI is advised. If there is concern about radiation exposure at CT, MRI may be used instead of CT in selected instances.

Endoscopy, Laparoscopy: The utilization of these techniques for objective tumor evaluation is not advised. However, such techniques may be useful to confirm complete pathological response when

biopsies are obtained or to determine relapse in trials where recurrence following complete response (CR) or surgical resection is an endpoint.

Tumor markers: Tumor markers alone cannot be used to assess response. If markers are initially above the upper normal limit, they must normalize for a participant to be considered in complete clinical response.

Cytology, Histology: These techniques can be used to differentiate between partial responses (PR) and complete responses (CR) in rare cases (e.g., residual lesions in tumor types, such as germ cell tumors, where known residual benign tumors can remain).

The cytological confirmation of the neoplastic origin of any effusion that appears or worsens during treatment when the measurable tumor has met criteria for response or stable disease is **mandatory** to differentiate between response or stable disease (an effusion may be a side effect of the treatment) and progressive disease.

FDG-PET: While FDG-PET response assessments need additional study, it is sometimes reasonable to incorporate the use of FDG-PET scanning to complement CT scanning in assessment of progression (particularly possible ‘new’ disease). New lesions on the basis of FDG-PET imaging can be identified according to the following algorithm:

- a. Negative FDG-PET at baseline, with a positive FDG-PET at follow-up is a sign of PD based on a new lesion.
- b. No FDG-PET at baseline and a positive FDG-PET at follow-up: If the positive FDG-PET at follow-up corresponds to a new site of disease confirmed by CT, this is PD. If the positive FDG-PET at follow-up is not confirmed as a new site of disease on CT, additional follow-up CT scans are needed to determine if there is truly progression occurring at that site (if so, the date of PD will be the date of the initial abnormal FDG-PET scan). If the positive FDG-PET at follow-up corresponds to a pre-existing site of disease on CT that is not progressing on the basis of the anatomic images, this is not PD.
- c. FDG-PET may be used to upgrade a response to a CR in a manner similar to a biopsy in cases where a residual radiographic abnormality is thought to represent fibrosis or scarring. The use of FDG-PET in this circumstance should be prospectively described in the protocol and supported by disease-specific medical literature for the indication. However, it must be acknowledged that both approaches may lead to false positive CR due to limitations of FDG-PET and biopsy resolution/sensitivity.

Note: A ‘positive’ FDG-PET scan lesion means one which is FDG avid with an uptake greater than twice that of the surrounding tissue on the attenuation corrected image.

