2 ELIGIBILITY ASSESSMENT AND ENROLLMENT

2.1 ELIGIBILITY CRITERIA

2.1.1 Inclusion Criteria

- 2.1.1.1 Histologically or cytologically confirmed recurrent or metastatic ONB not amenable to potentially curative local therapies. Review of tissue samples by Pathology at the NIH is preferred.
- 2.1.1.2 Participants must have measurable disease, per RECIST 1.1. See Section [6.3](#) for the evaluation of measurable disease. A previously treated lesion by radiotherapy can be chosen as the target lesion only if progression in the respective lesion has been demonstrated during or following radiotherapy.
- 2.1.1.3 Participants should have received at least one line of systemic therapy including a platinum agent, with evidence of disease progression clinically or radiographically.
- 2.1.1.4 Men or Women ≥ 18 years of age on day of signing informed consent. Because no dosing or adverse event data are currently available on the use of bintrafusp alfa in participants <18 years of age, children are excluded from this study.
- 2.1.1.5 ECOG performance status (PS) ≤ 2 (see [Appendix A](#)).
- 2.1.1.6 Participants must have adequate organ and marrow function as defined below:

Absolute neutrophil count (ANC)	$\geq 1,500/\text{mcL}$
Hemoglobin	$\geq 9 \text{ g/dL}$ (transfusions allowed)
Platelets	$\geq 100,000/\text{mcL}$
Serum Creatinine OR Measured CrCl or eGFR by CKD-EPI formula may be used to estimate CrCl/eGFR	$\leq 1.5 \times \text{ULN}$ OR $\geq 30 \text{ mL/min}/1.73\text{m}^2$ for participant with creatinine levels $> 1.5 \times$ institutional ULN
Serum total bilirubin OR Direct bilirubin	$\leq 1.5 \times$ upper limit of normal (ULN) OR $\leq \text{ULN}$ for participants with total bilirubin levels $> 1.5 \times \text{ULN}$
AST(SGOT) and ALT(SGPT)	$\leq 2.5 \times \text{ULN}$

2.1.1.7 The effects of immunotherapy on the developing human fetus are unknown. Therefore, participants must use effective methods of contraception (such as implants, injectables, combined oral contraceptives, IUDs, sexual abstinence or vasectomized partner).

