6.3.3.1 Target Lesions Evaluation

Complete Response (CR): Disappearance of all target lesions. Any pathological lymph nodes (whether target or non-target) must have reduction in short axis to <10 mm.

Partial Response (PR): At least a 30% decrease in the sum of the diameters of target lesions, taking as reference the baseline sum of diameters.

Progressive Disease (PD): At least a 20% increase in the sum of the diameters of target lesions, taking as reference the smallest sum on study (this includes the baseline sum if that is the smallest on study). In addition to the relative increase of 20%, the sum must also demonstrate an absolute increase of at least 5 mm. (Note: the appearance of one or more new lesions is also considered progression).

Stable Disease (SD): Neither sufficient shrinkage to qualify for PR nor sufficient increase to qualify for PD, taking as reference the smallest sum of diameters while on study.

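### Section 6.3.2 makes palpable lymph nodes measurable from 10 mm by calipers, while 6.3.1.1 classes nodes of 10 to <15 mm short axis as non-measurable; the two rules should be made one

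*Combined protocol and SAP*

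**What the plan says.** Four places in the combined protocol and SAP bear on nodal measurability.

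- Section 6.3.2, on clinical lesions: "Clinical lesions will only be considered measurable when they are superficial (e.g., skin nodules and palpable lymph nodes) and ≥ 10 mm diameter". The axis of the diameter is not named.
- Section 6.3.1.1, nodal paragraph: "a lymph node must be ≥ 15 mm in short axis when assessed by CT scan". Only the short axis is then to be followed.
- Section 6.3.1.1, non-measurable disease: the list includes "pathological lymph nodes with ≥ 10 to <15 mm short axis", with no imaging method attached.
- Section 6.3.1.1, general caliper line: "With calipers on clinical exam: ≥ 10 mm". Nodes are neither named nor excluded.

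The classification is used in two further places. Inclusion criterion 2.1.1.2 reads "Participants must have measurable disease, per RECIST 1.1" and refers to Section 6.3. Section 10.3.2 makes measurable disease at baseline a condition of being evaluable for response.

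For response, Section 6.3.3.1 says of CR: "Any pathological lymph nodes (whether target or non-target) must have reduction in short axis to <10 mm". No minimum change is set. PR needs a 30% fall in the sum of diameters, to which nodes contribute their short axis (6.3.1.2).

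**The concern.** A palpable node of, say, 11 mm short axis is measurable under 6.3.2 and non-measurable under 6.3.1.1. Two assessors could classify the same participant differently, and both would be following the protocol. If it is the only candidate target lesion, the choice decides whether the person is eligible and evaluable.

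The second issue is the distance between entry and response. The 15 mm rule leaves at least 5 mm between a target node and the nodal CR limit. The 10 mm caliper rule puts entry at that limit. A sole 11 mm target read at 9 mm has fallen by 2/11 = 18%, too little for PR, yet it meets the target CR size rule. Persisting non-target disease or a raised tumor marker does not remove the response: 6.3.3.2 classes these as Non-CR/Non-PD, and Appendix C turns target CR with Non-CR/Non-PD into an overall PR, which counts in the ORR.

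Because 6.3.2 does not name the axis, a node of 10 mm longest diameter could already be below 10 mm in short axis at baseline.

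ORR is the primary endpoint, and Section 10.2 treats 3 responses in 21 as enough to go on, so single misclassified responses matter.

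**Working it through.** **1. The plan's own figures (Section 10.2).** Stop if 0/12 respond; positive if at least 3/21.

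- Early termination at 5%: 0.95^12 = 0.540, matching the stated 54.0%.
- P(go | p) = sum over x = 1 to 12 of Bin(x; 12, p) × P(Y ≥ 3 − x), with Y ~ Bin(9, p).
- P(go | 0.05) = 0.0804, within the 0.10 limit. P(go | 0.20) = 0.803.

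**2. Smallest fall that counts as a response, sole target node.** For baseline B, PR needs a fall of 0.3 × B and CR needs a fall greater than B − 10 (at B = 10, any fall).

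| Baseline (mm) | Fall for PR (mm) | Fall for target CR (mm) |
|---|---|---|
| 10 | 3.0 | any (1 in whole mm) |
| 11 | 3.3 | more than 1 (2 in whole mm) |
| 12 | 3.6 | more than 2 (3 in whole mm) |
| 15 | 4.5 | more than 5 |

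For entry at 10-12 mm the CR route is therefore about 1-3 mm. With other target lesions present it closes unless they all disappear, because PR then needs 30% of the whole sum.

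**3. Illustration of false confirmed target CR.** The documents give neither reading error nor node sizes, so both are assumed: sole target node, no true change, independent normal reading error with SD 1.5 mm, entry reading 10 to <15 mm, and response defined as two consecutive readings below 10 mm.

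| Assumed true size | Over 2 assessments | Over 6 assessments |
|---|---|---|
| Flat, 5-25 mm | about 8% | about 18% |
| As above, only nodes truly ≥ 10 mm | about 2.5% | about 9% |

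With SD 1 to 2 mm, the first row runs 6%-11% and 12%-24%. For entry readings of 15-20 mm the rate is at most about 0.5%. In the first row, nodes truly below 10 mm are 12% of entrants but give 74% of the false responses over two assessments and 58% over six, so the size assumption drives the result. Six assessments at 8-week intervals means about 48 weeks without progression.

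**4. Effect on the decision rule.** Suppose a share s = 0.10 enters this way (an assumption), with false rate f among those who would not otherwise respond. The null ORR becomes 0.05 + s × f × 0.95.

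| f | Null ORR | P(at least 3/21) |
|---|---|---|
| 0 | 5.0% | 8.0% |
| 2.5% | 5.2% | 9.0% |
| 8% | 5.8% | 11.1% |
| 18% | 6.7% | 15.5% |

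If the false rate instead replaces the 5% in that tenth, f = 18% gives 0.9 × 0.05 + 0.1 × 0.18 = 6.3% and P = 13.6%.

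**5. Leverage of one false response.** One in stage 1 makes passage to stage 2 certain (otherwise 1 − 0.540 = 46.0%). P(at least 3/21) becomes P(at least 2 of the other 20 at 5%) = 26.4%.

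**The case against.** The strongest reply is that other provisions nearly close this route.

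- Section 2.2.2 requires baseline imaging at NIH and uses the NIH reading for eligibility. An 11 mm neck node on that reading would normally be non-measurable.
- Section 6.3.2 prefers imaging unless a lesion cannot be imaged. Neck nodes can be, and neck CT or MRI is part of the schedule.
- Section 6.3 asks for CR or PR to be confirmed by repeat imaging, and 6.3.2 asks for the same method at baseline and follow-up. A node followed by calipers lacks imaging confirmation; a node followed by scan should have met the 15 mm CT rule at baseline.
- The dedicated nodal paragraph is a more natural authority than an example in parentheses.

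Most of this stands and makes the case uncommon. It does not settle the conflict. The imaging preference is not a requirement, Section 6.3 still lets the investigator choose physical examination findings as a response measure, and no sentence says which nodal rule prevails. It might also be said that the 15 mm rule is written for CT only. However, the sentence classing 10 to <15 mm nodes as non-measurable carries no such limit.

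A reader might infer prevalence from Section 1.2.1, which reports neck-node recurrence in up to 20-30%. That describes ONB generally, not the share whose sole target is a 10-14 mm node followed by calipers, so it supports plausibility only.

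**Conclusion.** The inconsistency is real, and as written it can change who is eligible, who is evaluable and what counts as a response. The 1-3 mm route follows directly from the protocol's rules, but only for a sole target node or when all other targets disappear.

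The size of the effect on the ORR is not established. Under the assumptions above, with 1 participant in 10 entering this way, the null probability of a positive result is roughly 9% to 15.5%, against 8.0% as designed and a 10% limit. The upper end needs the flat 5-25 mm size assumption and about 48 weeks without progression, in participants enrolled after progression on platinum-containing therapy. If no such participant enrols, there is no effect.

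A reader might conclude that the type I error is about 17%. That comes only from rounding a null ORR of 6.7% up to 7%. More broadly, the documents do not support a claim that the design's error rate is breached, because they give neither the frequency of such nodes nor the reading error. This is a low-severity consistency correction.

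**What to change.** Make three linked wording changes:

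1. In 6.3.2, remove palpable lymph nodes from the examples of lesions measurable by calipers.
2. In 6.3.1.1, limit the caliper line to non-nodal superficial lesions.
3. State once that lymph nodes, palpable or not, are target lesions only if at least 15 mm in short axis on CT or MRI, and are followed by short axis on imaging. This extends the existing 6.3.1.1 rule to every method of detection and names MRI beside CT.

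This also removes the doubt over how a caliper-followed node would be confirmed by imaging. No procedure is added, since neck CT or MRI is already scheduled. The cost is that a rare candidate whose only lesion is a palpable node of 10 to <15 mm short axis would not be eligible, as 6.3.1.1 already implies.

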6.3.3 Response Criteria

Tumor responses to treatment will be assigned based on the evaluation of the response of target, non-target, and new lesions according to RECIST 1.1.

6.3.3.1 Target Lesions Evaluation

Complete Response (CR): Disappearance of all target lesions. Any pathological lymph nodes (whether target or non-target) must have reduction in short axis to <10 mm.

Partial Response (PR): At least a 30% decrease in the sum of the diameters of target lesions, taking as reference the baseline sum of diameters.

Progressive Disease (PD): At least a 20% increase in the sum of the diameters of target lesions, taking as reference the smallest sum on study (this includes the baseline sum if that is the smallest on study). In addition to the relative increase of 20%, the sum must also demonstrate an absolute increase of at least 5 mm. (Note: the appearance of one or more new lesions is also considered progression).

Stable Disease (SD): Neither sufficient shrinkage to qualify for PR nor sufficient increase to qualify for PD, taking as reference the smallest sum of diameters while on study.

6.3.3.2 Non-Target Lesions Evaluation

Complete Response (CR): Disappearance of all non-target lesions and normalization of tumor marker level. All lymph nodes must be non-pathological in size (<10 mm short axis).

Note: If tumor markers are initially above the upper normal limit, they must normalize for a participant to be considered in complete clinical response.

Non-CR/Non-PD: Persistence of one or more non-target lesion(s) and/or maintenance of tumor marker level above the normal limits.

Progressive Disease (PD): Appearance of one or more new lesions and/or *unequivocal progression* of existing non-target lesions. *Unequivocal progression* should not normally trump target lesion status. It must be representative of overall disease status change, *not a single lesion increase*.

Although a clear progression of “non-target” lesions only is exceptional, the opinion of the treating physician should prevail in such circumstances, and the progression status should be confirmed at a later time by the review panel (or Principal Investigator).

6.3.4 Evaluation of Best Overall Response

The best overall response is the best response recorded from the start of the treatment until disease progression/recurrence (taking as reference for progressive disease the smallest measurements recorded since the treatment started). The participant’s best response assignment will depend on the achievement of both measurement and confirmation criteria (See [Appendix C](#): Best Overall Response per RECIST 1.1).

6.3.5 Duration of Response

Duration of overall response: The duration of overall response is measured from the time measurement criteria are met for CR or PR (whichever is first recorded) until the first date that recurrent or progressive disease is objectively documented (taking as reference for progressive disease the smallest measurements recorded since the treatment started).

The duration of overall CR is measured from the time measurement criteria are first met for CR until the first date that progressive disease is objectively documented.

Duration of stable disease: Stable disease is measured from the start of the treatment until the criteria for progression are met, taking as reference the smallest measurements recorded since the treatment started, including the baseline measurements.

